9.3. Laboratory Evaluations

Clinical laboratory test values (hematology, serum chemistry, and urinalysis) and changes from baseline will be summarized by each visit and subgroup, ie, sex (male, female), ERT status (ERT naïve, ERT experienced), and overall if feasible for the enrolled population. By-visit summary will also include the last post-baseline values.

In addition, the following clinical summaries will be presented:

- Tables summarizing the frequencies and percentages of potential clinically significant (PCS; see Table 2) abnormalities at any time. The summary will indicate the number of subjects with PCS-low or PCS-high values at any time during treatment with migalastat but will not be presented by visit. PCS abnormalities will be determined both by investigator assessment and derivation from lab alert ranges provided by Amicus. PCS abnormalities that occur at unscheduled visits will be included.
- Tables displaying shifts from baseline to each assessment time-point, including the last postbaseline assessment, in laboratory test values from normal to high or low using normal range including eGFR, urine protein, and albumin.

Unscheduled visits will be included in PCS summaries and when determining the worst post-baseline assessment.

By-subject safety laboratory listings will be generated incorporating information and assessment results obtained from the designated laboratory which provided normal range and reported out of range flags. All laboratory results in Système International (SI) units will be presented in data listings. Tests will be listed in alphabetical order within their respective panels (hematology, serum chemistry, and urinalysis). Abnormal values will be flagged.

Chemistry		Hematology	
Alkaline Phosphatase	\geq 3 x Upper Limit Normal	II	$\leq 11.5 \text{ g/dL} \text{ (male)}$
AST	\geq 3 x Upper Limit Normal	Hemoglobin	\leq 9.5 g/dL (female)
ALT	\geq 3 x Upper Limit Normal	Hematocrit	$\leq 37\%$ (male)
BUN	\geq 30 mg/dL	петаюсти	$\leq 32\%$ (female)
Creatinine	$\geq 2.0 \text{ mg/dL}$	RBC count (absolute)	$<3.8 \ 10^{6}/uL \text{ or} > 5.5 \ 10^{6}/uL$
СРК	CPK $\geq 2 x$ Upper Limit Normal		$<4.5 \ 10^{3}/\text{uL} \text{ or } >13.5 \ 10^{3}/\text{uL}$
Gamma glutamyl transferase	$\geq 2 \text{ x Upper Limit Normal}$	Neutrophils	≤ 15%
Lactate dehydrogenase	\geq 300 U/L	Eosinophils	>0.7 10 ³ /uL
Glucose	\geq 100 mg/dL (fasting)	Platelet count	$\leq 75 \ 10^3/uL \text{ or } \geq 750 \ 10^3/uL$
Glucose	\geq 200 mg/dL (non-fasting)	Urinalysis Parameter	
Chloride	< 95 mmol/L or > 110 mmol/L	Protein	Increase of ≥ 2 units
Calcium	\leq 8.2 mg/dL or \geq 12 mg/dL	Albumin or microalbumin	Increase of ≥ 2 units
Magnesium	<1.4 mg/dL or > 2.7 mg/dL	Glucose	Increase of ≥ 2 units
Phosphorous	<2 mg/dL or >6 mg/dL		
Potassium	<3 mmol or > 6 mmol		
Protein, total	<5 g/dL or > 9 g/dL		
Sodium	< 130 mmol/L or > 150 mmol/L]	
TT ' A '1	\geq 10.5 mg/dL (male)		
Uric Acid	\geq 8.5 mg/dL (female)		

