11.4.4.3. Laboratory Data

Actual values and changes from baseline for clinical laboratory test results will be summarized using descriptive statistics (number, mean, median, minimum, and maximum). Categorical variables will be presented by number (percentage). Shift tables will also be provided for clinical laboratory tests.

Potentially clinically significant (PCS) laboratory values will be summarized by laboratory parameter. The PCS criteria for laboratory values will be defined in the final SAP. The summary will indicate the number of subjects with PCS-low or PCS-high values at any time during treatment with migalastat, but will not be presented by visit. It is possible for subjects to appear in both categories (PCS-low and PCS-high) for any parameter. The incidence rates of PCS values will be presented. There will be no statistical testing.

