3.6. Study Procedures and Flowchart

Table 1 details the schedule of assessments:

Table 1. Schedule of Assessments

Assessments	Baseline ^a		Treatment Period					EOT/ ET	Follow- up		
Visit Interval	Day 1	Month 3 (TC)	Month 6	Month 9 (TC)	Month 12	Month 15 (TC)	Month 18	Month 21 (TC)	Month 24		30-Day Safety
Visit Window (days)	—	±6	±6	±6	±6	±6	±6	±6	±6	±6	±6
Informed consent/assent	х										
Inclusion/exclusion criteria	х										
Medical history	х										
Concomitant medications	х	Х	х	х	х	Х	Х	х	х	х	
Dosing diary ^b	х	\rightarrow	\rightarrow	\rightarrow	\rightarrow	\rightarrow	\rightarrow	\rightarrow	х		
FPHPQ questionnaire	х		х		Х		х		х	х	
PedsQL	х		х		Х		х		х	х	
Complete physical examination	х		х		Х		Х		Х	х	
Adverse events		Х	х	х	Х	х	Х	х	х	х	х
Vital signs (BP, HR, RR, Temp)	х		х		Х		Х		х	х	
Body weight	х		х		Х		х		х	х	
Height	Х		х		Х		Х		х	х	
Tanner Staging	х		х		Х		Х		х	х	
12-lead ECG	х		х		Х		Х		х	х	

Assessments	Baseline ^a		Treatment Period							EOT/ ET	Follow-up
Visit Interval	Day 1	Month 3 (TC)	Month 6	Month 9 (TC)	Month 12	Month 15 (TC)	Month 18	Month 21 (TC)	Month 24		30-Day Safety
Visit Window (days)	—	±6	±6	±6	±6	±6	±6	±6	±6	±6	+6
Chemistry (including eGFR using Schwartz formula)	х		х		Х		Х		Х	Х	
Hematology	х		х		х		х		х	х	
Plasma lyso-Gb ₃ , analogs, and exploratory PD biomarkers	Х		Х		х		х		х	Х	
Urinalysis (urine protein, albumin and microalbumin levels)	х		х		х		х		х	Х	
Urine pregnancy test or date of LMP (as applicable)°	х	х	Х	Х	Х	х	Х	х	Х	Х	X
Echocardiogram (LVMi and additional parameters)	х				Х				Х	Х	
Study treatment supply/resupply/ return	х		х		х		х		Х	Xd	

Table 1. Schedule of Assessments (Continued)

Abbreviations: BP = blood pressure; ECG = electrocardiogram; eGFR = estimated glomerular filtration rate; EOT = end of treatment; ET = early termination; FPHPQ = Fabry-Specific Pediatric Health and Pain Questionnaire; HR = heart rate; LMP = last menstrual period; LVMi = left ventricular mass index; lyso-Gb₃ = Globotriaosylsphingosine; PD = pharmacodynamic; PedsQL = Pediatric Quality of Life Inventory; RR = respiration rate; TC = telephone call; Temp = body temperature

Note: Following Month 24, visits will continue every 6 months with interim telephone contacts at 3-month intervals. The assessment schedule will repeat starting from Month 3. Note: For the purposes of this study, a month is considered to be 30 days.

^a End of study assessments from Study AT1001-020 will be used as baseline assessments for Study AT1001-036.

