9.4. Vital Signs, Body Weight and Height

Vital signs (blood pressure, pulse rate, respiratory rate, and body temperature), height, and weight will be assessed at the scheduled visits specified in Section 4.6.

A summary table of observed and change from baseline values will be provided at each scheduled visit for the enrolled population, from baseline at Month 3, Month 6, Month 9, and Month 12 and by each subgroup, ie, sex (male, female), ERT status (ERT naïve, ERT experienced), and overall if feasible for the enrolled population. By-visit summary will also include the last post-baseline values.

The incidence rates of PCS vital sign values and changes from baseline (Table 3), by parameter, will be summarized. The summary will indicate the number and percentage of subjects with PCS-low and PCS-high values at any time during treatment and will not be presented by visit.

A by-subject listing will be provided for each vital sign parameter.

Parameter	Baseline PCS Criterion	Post-Baseline PCS Criterion	
Heart Rate	≥100 bpm (high)	≥100 bpm and CFB ≥15 (high)	
Healt Rate	≤60 bpm (l ow)	≤60 bpm and CFB ≤-15 (low)	
Diastolic Blood Pressure	≥83 mmHg (high)	≥83 mmHg and CFB ≥15 (high)	
Diastolic Blood Pressure	≤64 mmHg (low)	≤64 mmHg and CFB ≤-15 (low)	
Svotolia Plaad Procesure	≥131 mmHg (high)	≥131 mmHg and CFB ≥20 (high)	
Systolic Blood Pressure	≤110 mmHg (low)	≤110 mmHg and CFB ≤-20 (low)	
Maight	NA	Percent CFB ≥7% (high)	
Weight		Percent CFB ≤-7% (low)	

Table 3. Vital Signs Potentially	Clinically Significant Values
----------------------------------	-------------------------------

*CFB = change from baseline

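### For chemistry and hematology, the laboratory PCS table does not show whether a subject already met the criterion at the 036 baseline, so persistent and new abnormalities are counted together

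*SAP*

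**What the plan says.** **Counting rule.** SAP 9.3 gives the "number of subjects with PCS-low or PCS-high values at any time during treatment with migalastat but will not be presented by visit". Protocol 11.4.4.3 has the same rule: "number of subjects with PCS-low or PCS-high values at any time during treatment with migalastat, but will not be presented by visit". The protocol adds that incidence rates will be presented and that nothing will be tested. SAP 9.3 also specifies that "PCS abnormalities that occur at unscheduled visits will be included". Neither document excludes, separates or displays subjects who met the criterion at baseline.

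**Criteria.** In SAP Table 2 the blood criteria are levels; sodium, for example, is "< 130 mmol/L or > 150 mmol/L". The three urinalysis rows (protein, albumin or microalbumin, glucose) are changes instead, "Increase of ≥ 2 units", but the value from which the increase is measured is not named.

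**Baseline.** SAP 5.5 takes the last non-missing value on or before the first 036 dose. Footnote a of the schedule in SAP 3.6 says "End of study assessments from Study AT1001-020 will be used as baseline assessments for Study AT1001-036", so baseline normally follows a period on migalastat.

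**Related displays.** SAP 9.3 also plans change-from-baseline summaries, by-subject listings with abnormal values flagged, and "Tables displaying shifts from baseline to each assessment time-point, including the last postbaseline assessment, in laboratory test values from normal to high or low", judged on the normal range. For vital signs, SAP Table 3 has a column headed "Post-Baseline PCS Criterion" beside a baseline criterion, and every post-baseline entry requires a change from baseline.

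**The concern.** Long-term safety is the primary objective and there is no control group, so each subject's own baseline is the main reference for judging a laboratory finding. A table called an incidence should let the reader see what is new. On the blood rows, a subject who enters 036 beyond a limit and stays there is tabulated exactly like one who crosses it during the study. A reader of the study report could take a long-standing low count for an on-study finding, or dismiss a new one as probably long-standing. The plan treats this differently elsewhere: vital signs need a change from baseline, and a TEAE must begin on or after the first 036 dose (SAP 9.2).

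**Working it through.** **1. Which rows are affected.** Row count of SAP Table 2:

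| Panel | Rows | Form of criterion |
|---|---|---|
| Chemistry (glucose twice: fasting, non-fasting) | 18 | fixed limit or multiple of the upper limit of normal |
| Hematology | 7 | fixed limit |
| Urinalysis | 3 | increase |

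18 + 7 = 25 rows have no baseline element. One hematology row has lost its label in the available text; its units and Protocol Table 4 indicate the white cell count.

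**2. Do the shift tables fill the gap?** Take a hypothetical ALT that moves from 1.2 to 4 times the upper limit of normal. The PCS limit is 3 times, so this is a new PCS value. In a normal-range shift table it is high at both times and shows no shift.

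**3. Contrast with vital signs.** A systolic pressure of 135 mmHg at baseline and 138 later is above the 131 limit both times. The change is 138 − 135 = 3, below the required 20, so it is not counted as PCS after baseline. A hypothetical ALT steady at 3.2 times the upper limit of normal is counted.

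**4. Size.** The documents give no figure to reproduce: there is no sample size calculation (SAP 3.3) and no baseline PCS frequency. What follows is an illustration on assumed inputs. For one row and direction let

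- b = share of subjects PCS at the 036 baseline (assumed 5%, 10%, 20%)
- p = chance that such a subject is counted during treatment (assumed 0.5 or 1)
- i = new-onset proportion among the rest (assumed 5%)

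Reported proportion = b·p + (1 − b)·i. Share of counted subjects already PCS at baseline = b·p / [b·p + (1 − b)·i].

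| b | p | Reported | Share already PCS | New onset among those at risk |
|---|---|---|---|---|
| 5% | 0.5 | 7.25% | 34.5% | 5% |
| 5% | 1 | 9.75% | 51.3% | 5% |
| 10% | 0.5 | 9.5% | 52.6% | 5% |
| 10% | 1 | 14.5% | 69.0% | 5% |
| 20% | 0.5 | 14.0% | 71.4% | 5% |
| 20% | 1 | 24.0% | 83.3% | 5% |

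First row: 0.05 × 0.5 + 0.95 × 0.05 = 0.025 + 0.0475 = 0.0725, and 0.025 / 0.0725 = 0.345. Last row: 0.20 × 1 + 0.80 × 0.05 = 0.20 + 0.04 = 0.24, and 0.20 / 0.24 = 0.833.

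At the extreme with no new cases, three lasting abnormalities among an assumed 20 subjects give 3/20 = 15% in the table, against 0/17 among those not PCS at baseline.

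**5. The counting window.** SAP 9.3 does not say whether the baseline value itself falls within treatment. If a programmer included it, p would be 1 by construction. At b = 10% that is 14.5% rather than 9.5%, on the same data, compared with p = 0.5.

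**The case against.** The strongest defence is that the rule is deliberately inclusive. For long-term safety, every PCS value on treatment is of interest, and the only possible error is over-reporting. New cases always stay in the numerator, so a reader might infer that a signal is diluted, but it is not; it is only mixed with older findings.

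Nor is baseline status lost. The listings hold every value. Clinically significant laboratory abnormalities must be recorded as adverse events (Protocol 9.2.2.2.1), and conditions present at baseline count as such only if they worsen (Protocol 10.1.1), so the TEAE tables give a new-onset view. It would therefore be too strong to say that old and new abnormalities cannot be told apart. What remains is that the TEAE route depends on the investigator's judgement of significance rather than on the PCS limits, and that listings require a hand count.

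Three other inferences go too far:

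- **That the whole table lacks a baseline condition.** The urinalysis rows require an increase.
- **That the baseline value is certainly counted.** The schedule separates baseline from the treatment period, Protocol 9.1.2 puts baseline before the dose, and SAP 5.6.1.2 makes Day 1 of 036 the reference start for all analyses. The natural reading excludes it; the SAP just does not say so.
- **That Table 3 is a ready-made layout.** It lists criteria, specifies no baseline column in the output, and does not remove baseline-PCS subjects: systolic pressure of 135 then 156 (change 21) still counts.

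One objection shapes the remedy. Replacing the count with new onset alone would hide worsening in subjects already PCS, and an abnormality at the 036 baseline may itself have arisen on migalastat in AT1001-020.

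**Conclusion.** The point holds for the 25 chemistry and hematology rows. The PCS table combines abnormalities present at the 036 baseline with those that are new, under the name of incidence, and no planned summary table separates them at the PCS limits. Listings and TEAEs cover this in part.

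The size is unknown. The 7.3% to 24.0% range, against 5% new onset, rests wholly on the assumed b, p and i and shows only that the mixture could dominate a row. The display is descriptive and untested, so no formal conclusion is at risk; what is affected is how a primary-objective safety table is read. The change is worth making because it is small and specific. Present at the 036 baseline must not be read as present before migalastat.

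**What to change.** In SAP 9.3:

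1. State that the PCS count uses post-baseline 036 values, scheduled and unscheduled, and keep the any-time post-baseline count.
2. For each chemistry and hematology row, and separately for low and high, add the number of subjects PCS at the 036 baseline.
3. Beside it, give the number with new-onset PCS, over subjects not PCS at baseline who have at least one post-baseline value. Label it *new since 036 baseline*, not treatment-emergent, because baseline normally follows treatment in AT1001-020.
4. Name the 036 baseline as the reference for the three urinalysis increase criteria.
5. Record the addition in SAP section 12.

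Cost: SAP wording, extra columns, and denominators that vary by row. No new data are needed. Keeping the any-time count stays in line with Protocol 11.4.4.3. Worsening in a subject already PCS at baseline will not appear in the new-onset column and must still be read from the listings.

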9. STUDY ASSESSMENTS AND PROCEDURES

The schedule of study assessments and procedures is presented in Table 2. Total blood volume to be drawn per subject is presented in Table 3.

All study assessments should be conducted by the investigator, and/or a suitably qualified designee. Information will be recorded in the source documents and, where appropriate, the eCRF.

All assessments that occur during the study, where applicable and to the extent possible, should be completed during the designated visit, preferably in the order specified below. Once established, every effort should be made to maintain the order of procedures at each study visit throughout the study.

Assessments	Baseline ^a	line ^a Treatment Period						EOT/ ET	Follow-up		
Visit Interval	Day 1	Month 3 (TC)	Month 6	Month 9 (TC)	Month 12	Month 15 (TC)	Month 18	Month 21 (TC)	Month 24		30-Day Safety
Visit Window (days)		±6	±6	±6	±6	±6	±6	±6	±6	±6	+6
Informed consent/assent	Х										
Inclusion/exclusion criteria	Х										
Medical history	Х										
Concomitant medications	Х	Х	X	X	Х	Х	X	X	X	Х	
Dosing diary ^b	Х	\rightarrow	\rightarrow	\rightarrow	X	\rightarrow	\rightarrow	\rightarrow	X		
FPHPQ questionnaire	Х		X		Х		X		X	Х	
PedsQL	Х		X		Х		X		X	Х	
Complete physical examination	X		Х		Х		Х		X	X	
Adverse events		Х	X	X	X	Х	X	X	X	X	X
Vital signs (BP, HR, RR, Temp)	X		X		Х		X		X	X	
Body weight	Х		X		X		X		X	X	
Height	Х		X		X		X		X	X	
Tanner Staging	Х		X		Х		X		X	Х	
12-lead ECG	Х		X		X		X		X	X	
Chemistry (including eGFR using Schwartz formula)	X		Х		Х		Х		X	Х	
Hematology	Х		X		Х		X		X	Х	

Table 2:Schedule of Assessments

19 August 2021 Confidential

Assessments	Baseline ^a	Treatment Period					EOT/ ET	Follow-up			
Visit Interval	Day 1	Month 3 (TC)	Month 6	Month 9 (TC)	Month 12	Month 15 (TC)	Month 18	Month 21 (TC)	Month 24		30-Day Safety
Visit Window (days)		±6	±6	±6	±6	±6	±6	±6	±6	±6	+6
Plasma lyso-Gb ₃ , analogs, and exploratory PD biomarkers	X		Х		X		Х		Х	Х	
Urinalysis (urine protein, albumin and microalbumin levels)	X		Х		X		Х		Х	Х	
Urine pregnancy test or date of LMP (as applicable) ^c	X	Х	Х	X	X	Х	Х	Х	Х	Х	Х
Echocardiogram (LVMi and additional parameters)	X				X				Х	Х	
Study treatment supply/resupply/ return	X		Х		Х		Х		Х	X ^d	

Table 2:Schedule of Assessments (Continued)

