9.2.2.2. Clinical Laboratory Tests

9.2.2.2.1. Safety Laboratory Tests

Samples for chemistry, hematology, and urinalysis are outlined in Table 4. Laboratory samples collected on a dose administration day will be collected predose.

Chemistry	Hematology	Urinalysis
ALT	Hematocrit	Color
Alkaline phosphatase	Hemoglobin	Appearance
AST	Platelet count	Specific gravity
Albumin	RBC count	рН
Bilirubin, total	WBC count (absolute)	Albumin
BUN	Automated WBC differential	Bilirubin
Calcium, total	Basophils	Blood
Carbon dioxide, total (bicarbonate)	Eosinophils	Glucose
Chloride	Lymphocytes	Ketones
СРК	Monocytes	Microalbumin
Creatinine, serum	Neutrophils	Microscopy of sediment
GGT		Nitrite
Glucose		Protein
Lactate dehydrogenase		WBCs
Magnesium		
Phosphorous		
Potassium		
Protein, total		
Sodium		
Uric acid		

Table 4:Clinical Laboratory Parameters

Abbreviations: ALT = alanine transaminase; AST = aspartate transaminase; BUN = blood urea nitrogen; CPK = creatine phosphokinase; GGT = gamma-glutamyltransferase; RBC = red blood cell; WBC = white blood cell

Safety laboratory tests will be performed at a central laboratory. Instructions for the collection, processing, and shipment of clinical laboratory samples will be provided in the Laboratory Manual.

The investigator or a designee will review laboratory results and assess any out-of-range laboratory results as "not clinically significant" or "clinically significant." Any results that are considered clinically significant may be confirmed in a repeat test at the investigator's discretion. The investigator should consider repeat testing of persistent clinically significant results until the analyte returns to normal levels or until an etiology is determined. The investigator or a designee will sign and date all laboratory reports.

Clinically significant laboratory abnormalities must be captured as AEs or SAEs, as appropriate.

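### SAP Table 2 sets derived PCS limits for ALT, AST, ALP and GGT but none for total bilirubin, so the derived PCS count cannot show a bilirubin rise or a same-sample transaminase and bilirubin rise

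*SAP*

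**What the plan says.** Protocol 11.4.4.3 states that "Potentially clinically significant (PCS) laboratory values will be summarized by laboratory parameter" and that "The PCS criteria for laboratory values will be defined in the final SAP". The summary counts subjects with a low or high PCS value at any time on treatment and is not broken down by visit.

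SAP 9.3 takes this up. It promises "Tables summarizing the frequencies and percentages of potential clinically significant" abnormalities, points to SAP Table 2 for the criteria, brings in unscheduled visits, and adds that "PCS abnormalities will be determined both by investigator assessment and derivation from lab alert ranges provided by Amicus".

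In the chemistry block of SAP Table 2, alkaline phosphatase, AST and ALT each have a limit of at least "3 x Upper Limit Normal". The row for "Gamma glutamyl transferase" has a limit of at least 2 x ULN. There is no row for bilirubin and no row that combines two tests.

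Protocol Table 4 lists "Bilirubin, total" in the chemistry panel. The schedules (Protocol Table 2, SAP Table 1) place chemistry at baseline, Months 6, 12, 18 and 24, and the EOT/ET visit.

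**The concern.** Long-term safety is the primary objective. The PCS table is the only planned laboratory summary that counts subjects by the size of an abnormality at any time, with unscheduled samples included. In its derived part, a subject with ALT above the limit and raised bilirubin in the same sample is counted exactly like a subject with an isolated ALT rise. A subject with raised bilirubin alone meets no Table 2 criterion.

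Reading the enzymes and bilirubin together is a general convention in laboratory safety review. It is not a requirement in these documents, which name no hepatic concern with migalastat. What is at stake is how easily a reader of the summary tables could see such a pattern if it occurred. No estimate or test is affected.

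**Working it through.** The plan states no figure to reproduce, so the check sets the tables side by side.

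1. Inputs: the chemistry column of Protocol Table 4, the chemistry rows of SAP Table 2, the tabulation rules in Protocol 11.4.4.3 and SAP 9.3, and the visit rules in SAP 5.6.1.5.

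2. Liver tests measured against derived limits:
   - ALT: measured; limit at least 3 x ULN.
   - AST: measured; limit at least 3 x ULN.
   - ALP: measured; limit at least 3 x ULN.
   - GGT: measured; limit at least 2 x ULN.
   - Total bilirubin: measured; no limit.

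   That is 4 of 5 with a limit and 5 - 4 = 1 without. The chemistry rows run on without a visible break, so nothing suggests that a bilirubin row was lost when the text was read from PDF.

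3. Effect of the missing row. Take three hypothetical subjects: A has ALT at least 3 x ULN with raised bilirubin in one sample, B has the same ALT rise alone, and C has raised bilirubin alone. The derived count shows ALT = 2 (A and B) and nothing for bilirubin. A and B look alike, and C does not appear.

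4. Would a bilirubin row be enough? Compare two hypothetical cohorts. In the first, one subject has both rises in one sample and another has neither. In the second, one subject has only the ALT rise and another only the bilirubin rise. With a bilirubin row added, both cohorts give ALT = 1 and bilirubin = 1. Counts by parameter cannot separate them. Even one subject counted in both rows could have had the two rises at different visits. So the missing limit explains why bilirubin is not counted, while tabulation by parameter and not by visit explains why concurrence is not shown. Both need attention.

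5. Where bilirubin still appears:
   - By-visit summaries of values and changes (SAP 9.3), with minimum and maximum (SAP 5.4.1). These use nominal visits and the earliest value at a visit (SAP 5.6.1.5), so a peak in a repeat or unscheduled sample would not set the maximum.
   - Shift tables against the normal range (SAP 9.3), one test at a time and without grading the rise.
   - By-subject listings with abnormal values flagged, tests in alphabetical order within panel (SAP 9.3). Coincident rises can be found there by reading across.
   - Adverse events, since clinically significant laboratory abnormalities must be captured as such (Protocol 9.2.2.2.1).

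**The case against.** A reader might infer that the PCS tables cannot show bilirubin at all. The documents do not support that. SAP 9.3 gives investigator assessment as a second route to PCS status, and Protocol 9.2.2.2.1 has the investigator or a designee rate every out-of-range result as clinically significant or not. SAP 9.3 also refers to sponsor alert ranges. If these go beyond Table 2 they may include bilirubin; the documents do not show them, so this cannot be settled here. This part of the objection stands, and it limits the point to the criteria printed in Table 2.

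A reader might also infer a broken commitment. Protocol 11.4.4.3 promises a PCS summary by parameter with criteria in the SAP; it does not promise a limit for every analyte. The SAP is selective elsewhere: lymphocytes, monocytes and basophils have no row in Table 2, and respiratory rate and temperature have none in Table 3. This stands too.

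Finally, in a descriptive extension confined to subjects from one earlier study, listing review is a reasonable tool, and the listings hold all the values needed. That lowers the severity. It does not remove the point: the reader has to find coincident rises by hand, while the one display meant to count large abnormalities covers four liver tests and leaves out the fifth without giving a reason.

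**Conclusion.** The point holds as a minor, inexpensive improvement. As Table 2 is written, the derived part of the PCS summary cannot count a bilirubin rise, and its layout by parameter cannot show a transaminase and a bilirubin rise in the same sample. One of five liver tests is affected, in one display. Bilirubin is not lost from reporting, and no protocol commitment is broken.

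The conclusion assumes that programmers will apply Table 2 as printed. If the sponsor's alert ranges already contain a bilirubin limit, the first half of the gap closes in practice, but the second half remains. Neither half depends on which bilirubin cut-off is chosen.

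**What to change.** Add two rows to SAP Table 2:

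- a total bilirubin row;
- one subject-level row counting subjects with ALT or AST at least 3 x ULN together with raised bilirubin in the same sample, scheduled or unscheduled, with a listing of those subjects.

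The transaminase limit is the one already in Table 2. The bilirubin cut-off is not in the documents. At least 2 x ULN is one example, and any value above the ULN could serve. A lower cut-off flags more subjects, including more benign rises. The sponsor should set it and state it as an analysis flag; it is not a rule for clinical management. If the alert ranges already give a bilirubin limit, that value can be copied into Table 2.

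The cost is two table rows and a short listing, with possible flags from benign bilirubin rises. The data are already collected, so no new sampling is needed.

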11.2. Sample Size Considerations

Since this is a long-term extension study that will enroll subjects from Study AT1001-020, no formal sample size calculation was performed.

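### SAP Table 2 flags neutrophils by percentage only, so the absolute count at which the derived PCS flag fires varies threefold (0.675 to 2.025 x10^3/uL) across the unflagged WBC range

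*SAP*

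**What the plan says.** Protocol Section 11.4.4.3 leaves the laboratory PCS criteria to the SAP and says that incidence rates of PCS values will be presented, without statistical testing. SAP Section 9.3, Table 2 supplies the criteria. For neutrophils the whole entry is "Neutrophils ≤ 15" per cent. It works on the low side only and has no accompanying absolute count.

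The other cell-count rows in the haematology block are absolute. The eosinophil row begins "Eosinophils >0.7 10" and is in 10^3/uL. Platelets and RBC also have absolute limits. One further row has limits of below 4.5 or above 13.5 x10^3/uL. Its label did not survive extraction, and its units, range and position indicate total WBC. Neither document gives an absolute neutrophil criterion anywhere else.

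Protocol Section 9.2.2.2.1, Table 4 lists both "WBC count (absolute") and an "Automated WBC differential" that includes neutrophils.

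Table 2 is not the only input to PCS status. SAP Section 9.3 states: "PCS abnormalities will be determined both by investigator assessment and derivation from lab alert ranges provided by Amicus". The same section plans shift tables, described as showing changes "in laboratory test values from normal to high or low using normal range", and listings in which abnormal values are flagged.

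**The concern.** A percentage cut-off on one white-cell type has no fixed meaning as a count, because the count at which it fires moves with the total WBC. Two subjects whose WBC values are both unremarkable by Table 2 can be ordered the wrong way round: the one with more neutrophils is flagged and the one with fewer is not.

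Long-term safety is the primary objective. The PCS summary counts subjects with an abnormal value at any time during treatment and expressly includes unscheduled visits. If the derived neutrophil flag does not follow the neutrophil count, the incidence reported for that row is hard to interpret, and it is out of step with the eosinophil row beside it.

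**Working it through.** The documents state no absolute neutrophil figure, so there is nothing to reproduce. The check uses the limits in Table 2 itself.

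**Inputs**
- Neutrophil rule: PCS-low if the neutrophil percentage is 15 or less (SAP 9.3, Table 2).
- WBC rule: flagged if below 4.5 or above 13.5 x10^3/uL (same table; row label inferred). WBC from 4.5 to 13.5 is therefore unflagged.

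**Step 1. Absolute count at which the neutrophil rule fires.** Count = 0.15 x WBC.

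| WBC (10^3/uL) | Count at 15% (10^3/uL) |
|---|---|
| 4.5 | 0.675 |
| 5 | 0.75 |
| 6 | 0.90 |
| 8 | 1.20 |
| 10 | 1.50 |
| 13.5 | 2.025 |

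The ratio of the extremes is 2.025 / 0.675 = 3.

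**Step 2. Reversal of order, with no outside threshold.**
- Subject A: WBC 13.4, neutrophils 15%. Count = 13.4 x 0.15 = 2.01. The neutrophil row flags it and the WBC row does not.
- Subject B: WBC 4.6, neutrophils 16%. Count = 4.6 x 0.16 = 0.736. Neither row flags it.

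Subject A has 2.01 / 0.736 = 2.7 times the count of subject B, yet only A is flagged.

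**Step 3. How far the corner cases reach.** A count L passes both rows when WBC is at least 4.5 and below L / 0.15.
- L = 0.7: WBC from 4.5 to below 4.67.
- L = 1.0: WBC from 4.5 to below 6.67.
- L = 1.5: WBC from 4.5 to below 10.0.

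In the other direction, a count of 2.0 is flagged only when WBC is at least 2.0 / 0.15 = 13.33. These values of L are illustrations. The documents do not say which absolute count is low.

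**Step 4. Floor.** If WBC is 4.5 or more and the count is 0.675 or less, the percentage is at most 0.675 / 4.5 = 15%, so the neutrophil row fires. If WBC is below 4.5, the WBC row fires. Counts at or below 0.675 are therefore always caught by one of the two rows. Below WBC 4.5 the flag may be for low WBC and not for neutrophils: at WBC 3, for example, 15% is 0.45, and any count just above that passes the neutrophil row.

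**The case against.** A reader might infer that the plan would lose a low neutrophil count from the safety report, or that the PCS table is the only place where such a value is counted at any time. The documents do not support either reading:
- PCS status also rests on investigator assessment and on sponsor alert ranges. The documents do not say whether those ranges are the same as Table 2 or fuller, so subject B could still enter the PCS summary.
- Protocol Section 9.2.2.2.1 has every out-of-range result judged for clinical significance and requires significant ones to be captured as AEs or SAEs. SAP Section 9.2 then counts those that are treatment-emergent, whenever they occur.
- Shift tables against the normal range cover each time point and the last post-baseline assessment, and abnormal values are flagged in the listings.

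Three further objections are fair. The largest discrepancies occur only near the ends of the WBC range. Calling any particular count low needs a clinical threshold that the documents do not give. The study is also descriptive: the protocol says that "no formal sample size calculation was performed", PCS rates are not tested, and no decision rule hangs on the count. Neither the nonclinical nor the clinical safety summary in the protocol names a neutrophil signal.

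All of this limits the consequence, but none of it corrects the derived flag. The reversal in Step 2 needs no outside threshold. The backstops work alongside the derived Table 2 rule and do not change what it counts.

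**Conclusion.** The point holds for the derived Table 2 flag and for the incidence reported from it, and no further. Across the WBC range that the table leaves unflagged, the rule is equivalent to an absolute cut-off anywhere from 0.675 to 2.025 x10^3/uL, so it can mark a count of 2.01 and pass one of 0.74.

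The threefold figure assumes that the unlabelled row is WBC. The inconsistency itself does not depend on any view of which count is low. The importance is minor: this is a cheap gain in consistency for a study whose primary objective is safety.

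**What to change.** Add to SAP Table 2 an absolute neutrophil criterion in 10^3/uL, using the laboratory's reported count or, if that is not supplied, WBC x neutrophil percentage / 100. The sponsor's medical monitor should set the limit before database lock; the documents give no basis for proposing a figure here. Keep the percentage row, so that counts stay comparable with earlier studies if those used it (the documents do not say), and report the two rows separately.

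The cost is one extra table row and one derivation from data already collected, with no new procedures. A few more subjects may be flagged.
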